## Abbreviations

- ECDC European Centre for Disease Prevention and Control
- GP General practitioner
- ILI influenza-like illness
- MS Member States
- OROdds ratioPCVProportion of cases vaccinated
- PPV Proportion of population vaccinated
- VC Vaccination coverage
- VE Vaccine effectiveness
- (Tick/check mark indicates the sections that Member States should adapt and detail in their study annexes.)

# 1 Background

Influenza viruses constantly evolve, vaccines are reformulated every year. Therefore, vaccine effectiveness (VE) estimates from previous years cannot simply be carried over to subsequent years.

Conducting annual influenza VE estimates at the European level right at the beginning of a seasonal influenza epidemic/pandemic and monitoring VE along the course of the epidemic/pandemic is crucial in order to:

- decide on recommendations for the use of the vaccine;
- target complementary or alternative public health measures (e.g. antivirals) for segments of the population where the vaccine is less effective;
- allow more precise estimates of the impact of current vaccination strategies on the burden of disease to support vaccination campaigns;
- trigger further investigations on seasonal and pandemic vaccines (improve composition, use of adjuvants, need for booster doses);
- better manage and respond to expected reports of vaccine failures (especially during a pandemic); and
- counterbalance the reports of adverse events following immunisation by providing elements for adequate risk management and cost-effectiveness analysis.

The recent occurrence of the A(H1N1)v pandemic augments the importance of obtaining reliable and early vaccine effectiveness estimates for the pandemic vaccine. It takes approximately four to six months for the first supplies of strain-specific vaccines to become available once a new strain of influenza virus is identified and isolated. Consequently, by the time the vaccines are first administered, the virus already circulates and VE results are needed rapidly. In addition, vaccine availability is likely to increase over time – depending on vaccine production output and the licensing of additional vaccines, which means that IVE measurements need to be repeated over time during the pandemic. VE studies may help determining if the seasonal influenza vaccination is effective or interacts with pandemic vaccine in protecting against the A(H1N1)v virus.

Currently, only observational studies can be used to provide real-time estimates of influenza VE in Europe.

In order to provide early estimates of influenza VE, it is necessary to define which methods can be adopted in the European Union and the European Economic Area (EU/EEA) Member States. These methods have to take into account the specific situation of each Member State in terms of resources and available data. It is assumed that expertise developed during seasonal influenza season can be applied when measuring influenza VE during a pandemic.

During the 2008-09 influenza season, the European Centre for Disease Prevention and Control (ECDC) funded five pilot case-control studies (Portugal, Spain, Denmark, Romania, Hungary) — coordinated by EpiConcept — to measure influenza vaccine effectiveness in the elderly (>= 60 or >= 65 years old). The five pilot studies were based on GP surveillance networks. Four of them used the influenza-like illness (ILI) EU case definition. All of them included a common set of variables to adjust for positive and negative confounding.

The five case-control study teams met in Madrid in March 2009 to discuss the preliminary results of the pilot studies. One of the main limitations identified was the small sample size in each of the studies. The expert group recommended that the possibility of conducting a pooled analysis should be studied by using individual data from the pilot studies conducted in the 2008-09 season. In addition, it was suggested that a common core protocol for the 2009-10 season should be developed, including a pooled analysis to facilitate more precise VE estimates at the European level. The core protocol would determine the study design and the standard methods to be used in each of the studies (case definitions, exposure, outcome, minimum covariates to be collected, and their definition and coding).

This publication presents the core European protocol, outlining the agreed methods for measuring pandemic and seasonal VE for each of the individual studies. The protocol includes a proposed plan for pooled analysis. For groups interested in adhering to the core protocol, the specificities of each study will be detailed in the study annexes. Country-specific annexes will be developed by each study team. The collected variables, their definition, and the plan of analysis were revised based on the results of the pilot studies 2008-09, the recommendations of a workshop entitled 'Monitoring vaccine effectiveness during seasonal and pandemic influenza in EU' (Lisbon, 15 to 17 June 2009), and the state of knowledge on the pandemic in August 2009. The protocol will be updated according to a) the final vaccination strategy in each participating Member State (target groups, vaccine delivery, number of doses); b) the time the vaccine will become available; c) the extent of virus circulation; d) the identification of new groups at risk; and e) the potential clinical evolution of the A (H1N1)v infection. The study will be conducted in accordance with Good Epidemiological Practice (GEP) guidelines (http://www.dundee.ac.uk/iea/GEP07.htm).

# **2 Objectives**

## 2.1 Primary objectives

The primary objectives will be to measure in EU/EEA countries:

- pandemic influenza vaccine effectiveness in the target groups;
- seasonal influenza vaccine effectiveness among people aged 65 years and above in EU/EEA countries.

# 2.2 Secondary objectives

- Pandemic and seasonal vaccine:
  - to estimate pandemic and seasonal VE:
  - in each of the participating countries;
  - by risk groups.
- Seasonal vaccine:
  - to estimate VE by influenza subtype;
  - to provide intra-seasonal VE estimates;
  - to monitor VE every year.
- Pandemic vaccine:
  - to provide early VE estimates;
  - to estimate VE for one and two doses;
  - to estimate VE by vaccine brand.

# 3 Methods

## 3.1 Study design

- Case-control study in each participating country, with various sets of controls.
- Multicentre case-control study in several countries, with various sets of controls.

# 3.2 Study population

Residents (permanent or visitors) of the participating GPs catchment area.

- Seasonal vaccine: the study population will be community-dwelling individuals aged 65 years and above with no contra-indication for influenza vaccination.
- For the pandemic vaccines, the study population will be the population targeted by the vaccine with no contra-indication for vaccination with the pandemic vaccine.

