# 3.5 Cases

## ILI definition

A case of influenza like illness (ILI) will be defined as an individual who consults a participating GP, presenting a sudden onset of symptoms AND at least one of the following four systemic symptoms:

- fever or feverishness;
- malaise;

- headache;
- myalgia;

AND at least one of the following three respiratory symptoms:

- cough;
- sore throat; and
- shortness of breath.

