## 3.6 Case finding

#### **Case identification**

Cases will be identified among patients that present with ILI to a participating GP.

Following the procedures outlined by each study, all ILI cases (or a systematic sample of them) will be selected and asked to provide a nasal/throat swab specimen for influenza testing. Influenza-positive ILI cases will be considered as influenza cases.

**b** Descriptions of the GPs participating in each of the studies (number, distribution, catchment population) will be available in the study annexes.

**b** Descriptions of procedures on how to select ILI cases for swabbing in each of the targeted groups will be available in the study annexes.

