#### Case inclusion criteria

Cases are eligible if they meet the above case definition and accept to participate.

**b** Oral informed consent or written informed consent according to country procedures, as specified in the study annexes.

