# **3.7 Controls**

Various control groups can be selected depending on the available resources. All studies will include at least control group 1 (ILI influenza negative) as defined below.

- Seasonal vaccine: countries will assess whether other control groups could be used in addition to control group 1 (control group selection depends on feasibility).
- **b** The various control groups selected by each study will be detailed in the study annexes.
- Control group 1, ILI flu negative:
  - ILI cases that tested negative for influenza will be included in control group 1.
- Control group 2, non-ILI GP clients (density case-control design):
  - Controls will be selected among GP clients seen at the GP office and selected concurrently to cases (+/- one week from the date of consultation of the corresponding case). Controls will be selected by simple or systematic random sampling among clients who did not yet develop ILI during the influenza season.

**b** Procedures for selection in each of the studies will be detailed in the study annexes. If feasible, controls should be matched by age group (< 75 years; >= 75 years).

- Control group 3, GP clients (case-cohort design):
  - Controls will be selected randomly from a list of GP patients.
  - **b** Procedures for selection in each of the studies will be detailed in the study annexes.
- Control group 4, community controls (density case-control design):
  - Controls are randomly selected individuals living in the same geographical area (defined by postcode or other geographical/administrative division) as the corresponding case. Control individuals have not suffered from ILI during the current influenza season until the corresponding case became ill.
    - **P** Procedures for selection will be detailed in the study annexes.
    - If feasible, controls should be matched by age group (< 75 years; >= 75 years).
- Control group 5, community controls (case cohort):
  - Controls will be randomly selected individuals living in the same geographical area of the corresponding case.
    - **P** Procedures for selection will be detailed in the study annexes.
    - If feasible, controls may be matched by age group (< 75 years; >= 75 years).
- Control group 6, community controls (screening method):
  - For each of the target age groups, vaccine coverage of cases will be compared with the vaccine coverage of the population in the GP catchment area.

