#### Vaccination status ascertainment

The exposure of interest in this study will be vaccination history with trivalent influenza vaccine (for seasonal vaccine) and vaccination history with the pandemic vaccine (once the vaccine becomes available). The vaccination history includes date of administration and brand names. Documenting the flu batch codes will allow identifying the vaccine brand, the vaccine content (seasonal, pandemic) and the dose.

An individual is considered as vaccinated against influenza if:

- he or she reports having received an influenza vaccination during the current season; or
- he or she is registered as vaccinated in a vaccination registry;
- or
- his or her insurance company can show evidence of pharmacy delivery or re-imbursement of influenza vaccine/vaccination during the current influenza season.
- Pandemic vaccine: The number of doses will be documented.
  - **b** Seasonal and pandemic vaccines used will be detailed in the study annexes.
  - **b** The precise mode of vaccine ascertainment for each study will be specified in the study annexes.

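### Visitors may enter as cases, but the sources of optional control groups 3 to 5 need not cover them, and no variable marks them

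*Protocol*

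**What the plan says.** Section 3.2 describes the population as "Residents (permanent or visitors) of the participating GPs catchment area", so visitors are included by name.

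Entry as a case rests on consultation, symptoms, a positive test and consent. An ILI case is "an individual who consults a participating GP, presenting a sudden onset of symptoms" with the listed symptoms. Under Case identification, "Cases will be identified among patients that present with ILI to a participating GP". Under Case inclusion criteria, "Cases are eligible if they meet the above case definition and accept to participate". The case exclusion criteria cover refusal, contraindication, institutional residence and inability to consent or be interviewed. They do not mention place of residence or registration with the GP.

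The control sources in section 3.7 differ:

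- **Group 1** is compulsory: "All studies will include at least control group 1 (ILI influenza negative) as defined below". It comes from the same consultations as the cases: "ILI cases that tested negative for influenza will be included in control group 1".
- **Group 2** (optional) is sampled from clients seen at the GP office.
- **Group 3** (optional): "Controls will be selected randomly from a list of GP patients".
- **Groups 4 and 5** (optional) are randomly selected people living in the same area as the case. No sampling frame is named.

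Selection procedures for groups 2 to 5 are left to the study annexes. The collected information in section 3.12, the variable list in Annex 1 and the minimum dataset in Annex 2 contain no item on visitor status, residence or GP registration. The country and GP codes identify the study site, not where the patient lives.

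**The concern.** In a case-control study, the controls should show the vaccination coverage of the population that gave rise to the cases. If a visitor can be a case but cannot be drawn as a control, the coverage of cases includes people whom the control coverage does not describe. Any difference in coverage between visitors and the people on the frame then enters the odds ratio, and so VE = 1 - OR.

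The planned data cannot reveal or remove this. None of the covariates in the Annex 6 example model (age, sex, chronic disease, smoking, functional status, previous vaccination, hospitalisation, GP visits, week) identifies a visitor. Without a marker, visitors can be neither excluded nor examined in a sensitivity analysis.

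Two features give this practical weight. Section 3.13 pools separately by control group, so a shift in a group 3 to 5 estimate is not diluted by group 1 data. Section 4.7 proposes comparing results across all six control groups, where a difference caused by visitors could be read as an effect of the control design.

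**Working it through.** **Step 1. Who can appear on each side**

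| Comparison | Visitor can be a case | Visitor can be a control |
|---|---|---|
| Group 1, influenza-negative ILI | yes | yes, same consultations |
| Group 2, clients seen at the office | yes | yes, if consulting |
| Group 3, GP patient list | yes | doubtful; the protocol does not say whether the list holds temporary patients |
| Groups 4 and 5, living in the area | yes | depends on the frame, which is left to the annexes |

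**Step 2. Planning values**

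The protocol gives no figure for visitors. The stratified analysis text in section 3.13 assumes coverage of 50% and VE of 60% (OR 0.4). The same values give 89 cases and 89 controls in Tables 1 and 2 at 80% power. As a check on these values, a continuity-corrected two-proportion formula with case coverage 0.4 x 0.5 / (1 - 0.5 + 0.4 x 0.5) = 0.2857 gives 90, against the 89 stated. All 24 rows of Table 1 agree within 1. I use coverage of 50% and OR 0.4 below.

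**Step 3. Shift when visitors are among the cases only**

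Assumptions, not in the protocol: visitors are 5% or 10% of cases (s), and their coverage (c) is between 20% and 70%. The true OR of 0.4 holds in both groups, and controls have 50% coverage with no visitors.

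Coverage among cases arising from a group with coverage c: f(c) = 0.4c / (1 - c + 0.4c).

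- f(0.5) = 0.20 / 0.70 = 0.2857
- f(0.2) = 0.08 / 0.88 = 0.0909
- f(0.7) = 0.28 / 0.58 = 0.4828

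Mixed case coverage: p = (1 - s) x 0.2857 + s x f(c). Control odds are 0.5 / 0.5 = 1, so the apparent OR is p / (1 - p).

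| s | c | p | Apparent OR | Apparent VE |
|---|---|---|---|---|
| 5% | 20% | 0.2760 | 0.381 | 61.9% |
| 5% | 70% | 0.2956 | 0.420 | 58.0% |
| 10% | 20% | 0.2662 | 0.363 | 63.7% |
| 10% | 70% | 0.3054 | 0.440 | 56.0% |
| 5% or 10% | 50% | 0.2857 | 0.400 | 60.0% |

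For a vaccine with no effect (OR 1) and s = 10%:

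- c = 20%: case coverage 0.9 x 0.5 + 0.1 x 0.2 = 0.47, OR 0.47 / 0.53 = 0.887, apparent VE 11.3%
- c = 70%: case coverage 0.52, OR 0.52 / 0.48 = 1.083, apparent VE -8.3%

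**Step 4. Visitors on both sides (group 1)**

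Let 10% of controls be visitors with 20% coverage. Control coverage is 0.9 x 0.5 + 0.1 x 0.2 = 0.47, with odds 0.47 / 0.53. If the odds of influenza against other ILI in the unvaccinated are the same for visitors and residents, vaccinated and unvaccinated cases arise in the ratio 0.4 x 0.47 to 0.53, that is 0.188 / 0.53. The OR is 0.188 / 0.47 = 0.400, so there is no shift.

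**The case against.** The strongest reply is that this is a core protocol for several countries. Selection procedures are delegated to the annexes, which must define the control groups used, and Annex 1 allows variables to be added. Section 3.15 also asks each study to describe its cases and how their representativeness may affect VE. A study using group 3 could solve the problem itself. That is true, but the delegation is incomplete. Case eligibility and the minimum dataset are core text, section 4.4 wants European-level variables collected in the same way everywhere, and the annex checklist does not raise residence. An item that was not collected cannot be recovered at pooling.

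A second reply is that the effect is small beside random error. With 90 cases and 90 controls at the planning values, the standard error of log OR is sqrt(1/25.7 + 1/64.3 + 1/45 + 1/45) = 0.31, and the 95% interval for VE runs from about 26% to 78%. This stands, and it keeps the point minor. Pooling narrows that interval, however, and does not reduce the shift.

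Two stronger readings are tempting, and the protocol supports neither:

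- **A reader might infer that visitors are on none of the frames for groups 3 to 5.** Section 3.7 names no frame for groups 4 and 5, section 3.2 treats visitors as a kind of resident, and nothing says that the group 3 list omits temporary patients.
- **A reader might infer that visitors' doses are missed because they are recorded elsewhere.** The condition "he or she is registered as vaccinated in a vaccination registry" is only one of three alternatives in section 3.8. The patient's own report is another, so a visitor vaccinated elsewhere can still be counted as vaccinated.

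**Conclusion.** The point holds in a limited form. The core protocol admits visitors as cases, does not require the sources of optional control groups 3 to 5 to cover them, and records nothing that would identify them. A mismatch is likely for group 3 and possible for groups 4 and 5. Group 1, the only group required in every study, and group 2 are not affected by it.

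Under the assumed inputs, the shift at a true VE of 60% is about 2 points with 5% visitors and about 4 points with 10%. It can go in either direction and is zero if visitors' coverage equals residents'. Visitor share and visitor coverage are assumptions throughout, so the real size is unknown and may be negligible. This is a minor design improvement. It does not put the group 1 estimates in doubt.

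**What to change.** Add one yes/no item to Annex 1 and to the minimum dataset in Annex 2, worded to fit the frame: on this GP's patient list, or permanent resident of the area.

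State in section 3.7 that comparisons with groups 3 to 5 use only cases who could have been selected as controls from the frame actually used. For group 3, that means cases on the GP's list. Keep visitors in the comparisons with groups 1 and 2.

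The cost is one extra question, a filter in the analysis, and a few cases lost from optional comparisons.

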#### According to ECDC

(http://www.ecdc.europa.eu/en/publications/Publications/Forms/ECDC\_DispForm.aspx?ID=388; 25 August 2009), the target groups to be considered for the pandemic vaccine are:

- people aged less than 65 years with chronic underlying conditions, namely:
  - chronic respiratory diseases;
  - chronic cardiovascular diseases;
  - chronic metabolic disorders (notably diabetes);
  - chronic renal and hepatic diseases;
  - persons with deficient immunity (congenital or acquired);
  - chronic neurological or neuromuscular conditions;
  - any other condition that impairs a person's immunity or prejudices their respiratory function;
  - young children (especially under the age of 2 years); and
- pregnant women.

The target groups may differ between countries. Other risk groups may be included during the pandemic.

**b** Target groups for each study will be listed in the study annexes.

## 3.3 Study period

The study period will start when the influenza virus is circulating and the vaccine is available.

Seasonal vaccine: the study period will start at the beginning of the seasonal influenza period and finish at the end of the influenza period.

**b** Each study will define the beginning, the peak and the end of the study period according to the information provided by the country influenza sentinel surveillance system (details available in the study annexes).

- Pandemic vaccine: the study period will be defined depending on the gradual availability of vaccines and the pandemic incidence.
  - **b** Each study will define the beginning and end of the pandemic VE study period.

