# 3.8 Exposure (vaccination)

## **Definition of vaccination status**

Seasonal vaccine: An individual is considered as vaccinated against influenza if the vaccination occurred more than 14 days before disease onset or more than 14 days before being selected as a control.

- Pandemic vaccine: An individual is considered:
  - *fully vaccinated* if he/she has received two doses of the vaccine more than 14 days before developing ILI symptoms or before being selected as a control;
  - *partially vaccinated* if he/she has received:
     a) only one dose of the vaccine more than 14 days before developing ILI symptoms (or more than 14 days before being selected as a control);
     b) a second dose less than 15 days before developing ILI symptoms (or more than 14 days before being selected as a control);
  - *unvaccinated* if he/she has not received any vaccine or if he/she has received one dose less than 15 days before developing symptoms.

The definition of the vaccination status may be revised and should be taken into account in the analysis if preliminary clinical data indicate that one dose is sufficient to confer protection, or that the immunisation delay is different from the currently assumed 14 days.

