#### Table 3: Sample size interim analysis

Outputs	Sample size needed in pooled data	Sample size needed for each individual site
Pooled crude VE for all vaccines and target groups	90 cases*	
Pooled adjusted VE for all vaccines and target groups	90 cases*	
Pooled VE stratified by specific variables (e.g. age group, target group)	90 cases per stratum*	
Crude VE by study site for all vaccines and target groups		90 cases per study site
Pooled adjusted VE for all vaccines and target groups		90 cases per study site
Stratum-specific, site-specific VE (e.g. age group, target group		90 cases per study site and stratum
Pooled brand VE	90 cases for each specific brand analysis*	
Pooled brand analysis stratified by specific variables	90 cases per stratum for each specific brand analysis*	
Site-specific, brand-specific, stratum- specific VE (e.g. age group, target group)		90 cases per study site and stratum for each specific brand analysis

\* Using one-staged pooled analysis (see Annex 3 for further details)

The timing to conduct each interim analysis will depend on the time needed to reach the appropriate sample size. This will depend mainly on the ILI incidence, the influenza incidence, the vaccination coverage, and the swabbing scheme used by GPs and the number of GPs (see Excel calculator, attached to the PDF version of this document).

The sample size suggested for brand-specific VE is an estimate and cannot be precisely defined at this stage. The sample size for brand VE will depend on the vaccination coverage for each brand and therefore on the market share.

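### With no lag between vaccine availability and inclusion, the crude pandemic VE and the 90-case count take in ILI patients who cannot yet count as vaccinated

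*Protocol*

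**What the plan says.** Section 3.3 gives a general start rule: "The study period will start when the influenza virus is circulating and the vaccine is available". For the pandemic vaccine it adds that "the study period will be defined depending on the gradual availability of vaccines and the pandemic incidence" and that "Each study will define the beginning and end of the pandemic VE study period". It neither asks for nor rules out a lag between availability and inclusion.

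Section 3.8 counts one dose as partial vaccination only if the person received "only one dose of the vaccine more than 14 days before developing ILI symptoms". Full vaccination requires that "he/she has received two doses of the vaccine more than 14 days before developing ILI symptoms". A person is unvaccinated "if he/she has received one dose less than 15 days before developing symptoms".

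Section 1 expects that "by the time the vaccines are first administered, the virus already circulates and VE results are needed rapidly", so the early window will contain ILI patients. Section 3.7 makes influenza-negative ILI patients the one control group that every study must use.

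Table 3 (section 3.13) lists the pandemic interim outputs. The first is "Pooled crude VE for all vaccines and target groups", needing 90 cases, and there is also a crude VE by study site. The pooled adjusted VE carries the same 90-case threshold.

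Calendar time appears in three places: the pandemic time strata in section 3.13, the derived variable weekepi in Annex 5, and week indicators in the Annex 6 syntax. That syntax is written for seasvacc and described as guidance only. Section 3.10, which lists the confounders, does not name calendar time.

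**The concern.** Sections 3.3 and 3.8 do not fit together. If inclusion starts with availability and a dose counts only after 14 days, everyone with onset in the first 14 days is unvaccinated by definition. (I set aside anyone given two doses inside that window; the protocol states no dose interval.) These patients have no vaccinated counterparts from the same days, yet they are merged into the unvaccinated row of the crude table.

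The proportion of ILI patients who test positive changes as an epidemic wave passes. If it is higher in the window than later, the unvaccinated row gains too many cases and crude VE is too high. If it is lower, crude VE is too low. This happens even for a vaccine with no effect. The protocol wants early pandemic estimates to support decisions on vaccine use, so a distorted interim figure has consequences. The 90-case trigger can also be reached partly on records that say nothing about the vaccine.

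**Working it through.** **The plan's own figure.** Table 2 gives 89 cases and 89 controls for 50% coverage and OR 0.4. Coverage in cases is 0.4×0.5/(0.5+0.4×0.5) = 0.286. With alpha 0.05 (two-sided assumed), power 0.80 and 1:1 sampling, the two-proportion formula gives 81 per group without continuity correction and about 89.4 with it. The stated figure is reproduced, and it assumes 50% coverage across all counted controls.

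**Inputs not in the protocol (assumed).** 100 ILI patients per week; 2 weeks in the window with coverage 0; 6 later weeks with control coverage 30%; positivity among the unvaccinated moving between 50% and 30%.

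**Method.** In each period let o be the odds of positivity among the unvaccinated, c the control coverage and C the number of controls. The expected cells are:
- vaccinated cases: OR×o×C×c
- unvaccinated cases: o×C×(1−c)
- vaccinated controls: C×c
- unvaccinated controls: C×(1−c)

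Add the two periods and take the crude OR.

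**Positivity falling, 50% to 30%**
- Window: 100 cases and 100 controls, all unvaccinated.
- Later, null vaccine: cases 54 vaccinated and 126 not; controls 126 and 294.
- Merged: OR = (54×394)/(226×126) = 0.747, a spurious VE of 25%.
- With true OR 0.4: (22.8×410.8)/(233.2×133.2) = 0.302, VE 70% instead of 60%.

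**Positivity rising, 30% to 50%**
- Window: 60 cases and 140 controls, all unvaccinated.
- Null vaccine: (90×350)/(270×90) = 1.296, VE −30%.
- True OR 0.4: crude OR 0.510, VE 49%.

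**Constant positivity among the unvaccinated.** The crude OR equals the true OR, so there is no bias. Across the falling and rising scenarios the window supplies about 17% to 39% of all cases.

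**Wider range.** Take 50% later coverage, true OR 0.4, and overall positivity moving between 50% and 20%. With 10%, 25% or 50% of patients in the window:

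| Early share | Positivity falls | Positivity rises |
|---|---|---|
| 10% | VE 67% | VE 49% |
| 25% | VE 74% | VE 30% |
| 50% | VE 80% | VE −8% |

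**The 90-case trigger.** Let a share f of both the 90 cases and the 90 controls come from the window. Coverage becomes 0.286(1−f) in cases and 0.5(1−f) in controls. Power (normal approximation, no continuity correction) is:
- f = 0: 84%
- f = 10%: 78%
- f = 25%: 66%
- f = 50%: 44%

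At f = 25%, dropping the window leaves about 68 per group and power of 73%. Discarding those records does better than keeping them in the crude comparison.

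**Does leaving out the window suffice?** In the two-period model it returns the true OR exactly, but only because coverage and positivity are flat afterwards. Let coverage rise from 5% to 30% over weeks 3 to 8, and positivity fall linearly from 50% to 30% over the eight weeks. A null vaccine then shows crude VE of 23% with the window and 12% without it. With positivity rising from 30% to 50%, the figures are −28% and −12%. Restriction removes roughly half the bias; the rest needs adjustment for week.

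**The case against.** Several points on the other side stand.

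- **Dates.** A reader might infer that the protocol opens every pandemic study on the day vaccine arrives. It does not. Each study sets its own pandemic dates and could build in a lag; the study annexes are not part of the document. What stands is that the core protocol, whose purpose is common methods, does not ask for one.
- **Order of release.** A reader might infer that the crude VE is the first pandemic figure to be released. Table 3 gives crude and adjusted pooled VE the same 90-case threshold, and section 3.17 does not say that first estimates are crude. Annex 3 presents the one-stage model as the way to control confounders early in the season.
- **Role of early patients.** They are not only controls. They enter as influenza-positive cases and as influenza-negative controls, all in the unvaccinated category.
- **Other handling of time.** The strata by vaccine-availability period address this issue directly. With week indicators, weeks without vaccinated patients add essentially nothing to the VE estimate. The full covariate list may properly sit in a statistical analysis plan.
- **A crude OR is crude by definition.** It is equally unadjusted for age and chronic disease. That is true, but those factors do not make exposure impossible for a block of patients, nor do they erode the case count that releases the output.

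**Conclusion.** The point holds for the crude pandemic VE outputs in Table 3 and for the 90-case trigger. Following sections 3.3 and 3.8 as written, and absent a lag set by the study, patients who cannot be exposed enter the comparison. The bias arises only if positivity among the unvaccinated differs between the window and later. That is to be expected in an epidemic wave, but its direction depends on the phase. All sizes rest on assumed early share, positivity and coverage, none of which the protocol gives. In the main illustration a true VE of 60% reads as 70% or 49%.

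It would be too strong to conclude that the pandemic VE results as a whole are invalid. Adjusted VE with week indicators, or VE within the availability strata, is largely protected, so this is not a must-fix for the adjusted estimates. The weakness there is that week is only a derived variable and a term in guidance-only syntax for the seasonal vaccine. Seasonal VE has its own start rule and is outside this point, and Table 1 is unaffected. For two-dose VE the window without fully vaccinated patients is longer than 14 days by the dose interval.

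**What to change.** 1. In section 3.3, restrict pandemic VE analyses and the 90-case count to patients, cases and controls alike, with onset (or selection) at least 15 days after vaccine first became available to their target group in that study.
2. In Table 3, state that the headline pooled pandemic VE is adjusted at least for study and week of onset, with the crude VE shown beside it as descriptive only. This is needed because coverage keeps rising after the window and restriction alone leaves residual bias.

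The cost is about two sentences. Onset dates are already collected (section 3.12), and campaign start dates are already to be summarised by study (Annex 3). Availability dates specific to each target group would have to be recorded. The first interim analysis may come slightly later, but the records left out carry no information on vaccine effect.
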